APPENDIX 1: Quality of Life Questionnaire

Pre-op questionnaire version 1- 6th August 2009

[figure not shown]
[figure not shown]
DESCRIBING YOUR OWN HEALTH TODAY

Please indicate on this scale how good or bad your own health state is today.

The best health state you can imagine is marked 100 and the worst health state you can imagine is marked 0.

Please draw a line from box **A** to the point on the scale that best indicates how good or bad your health state is today.

A
Your own health state today

EQ-5D

Under each heading, please tick the ONE box that best describes your health TODAY

MOBILITY

- I have no problems in walking about
- I have slight problems in walking about
- I have moderate problems in walking about
- I have severe problems in walking about
- I am unable to walk about

SELF-CARE

- I have no problems washing or dressing myself
- I have slight problems washing or dressing myself
- I have moderate problems washing or dressing myself
- I have severe problems washing or dressing myself
- I am unable to wash or dress myself

USUAL ACTIVITIES *(e.g. work, study, housework, family or leisure activities)*

- I have no problems doing my usual activities
- I have slight problems doing my usual activities
- I have moderate problems doing my usual activities
- I have severe problems doing my usual activities
- I am unable to do my usual activities

PAIN / DISCOMFORT

- I have no pain or discomfort
- I have slight pain or discomfort
- I have moderate pain or discomfort
- I have severe pain or discomfort
- I have extreme pain or discomfort

ANXIETY / DEPRESSION

[figure not shown]
- I am not anxious or depressed
- I am slightly anxious or depressed
- I am moderately anxious or depressed
- I am severely anxious or depressed
- I am extremely anxious or depressed

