**Multicentre Randomised Controlled Trial of
Compression Therapy following Endovenous Thermal
Ablation of Varicose Veins**

FULL TITLE

A multicentre randomised controlled trial of compression therapy following endovenous thermal ablation of varicose veins.

SUMMARY

This study will be looking at the effect of compression therapy in patients having endovenous treatment for truncal incompetence of their varicose veins using either radiofrequency ablation (RFA) or endovenous laser therapy (EVLT). Patients will be randomised to either the compression group (group A) or the no compression group (group B).

The pain scores, compliance, quality of life scores, occlusion rate at 6 months as well as the cost effectiveness of each intervention will be assessed.

OBJECTIVES

- Primary Objective

Patient's pain score for the first 10 days post-procedure using the visual analogue scale (VAS)

- Secondary Objective

The secondary objectives would be to compare the two treatment groups with respect to:

- The quality of life scores at baseline, 2 weeks and 6 months using the EQ-5D, AVVQ and CIVIQ scores
- The clinical change using the VCSS at baseline, 2 weeks and 6 months
- The degree of bruising and phlebitis at 2 weeks and 6 months
- The patient compliance with the intervention
- The time taken to return to work and normal activities
- Occlusion rates at 6 months
- Comparison of the cost effectiveness of the intervention

Background

Varicose veins are common and are known to affect approximately one third of the population¹. Chronic venous disease (CVD) has been shown to have a negative impact on the quality of life of patients and treatment of varicose veins has been demonstrated to lead to improvement in the quality of life of patients²⁻⁴. Over the past decade, new endovenous techniques have been introduced and these are felt to be cost-effective, especially, when performed in an outpatient or 'office-based' setting⁵.

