Patients randomised to group A will be asked to wear compression stockings for 1 week.

Patients randomised to group B and undergoing endothermal ablation only will not be provided with any compression. However, if they receive adjuvant treatment to their tributaries, they will be provided with bandages to wear for 24 hours only, with no further compression afterwards.

At baseline, patients will be asked to fill quality of life questionnaires (EQ-5D, AVVQ and CIVIQ) and will have their clinical scores assessed (CEAP and VCSS). On discharge after their varicose vein intervention, they will then be provided with a diary to record their post-procedural pain every day for 10 days using a validated visual analogue scale (VAS) as well as to record when they return to their normal activities and are back to work. They will also be asked to attend a follow-up in 2 weeks and at 6 months.

Patients' GP will also be sent a letter to inform them of their patient's participation in the study.

Follow-up

Patients will be followed up in the outpatient clinic at 2 weeks and 6 months.

Follow-up at 2 Weeks

At the 2 weeks' follow-up, the diary containing details of the pain scores and how soon patients were able to return to normal activities/work will be collected. In addition, patients will be asked about any bruising or phlebitis they have had in the two weeks after their procedure and how compliant they have been with the compression. They will be examined and the Venous Clinical Severity Score (VCSS) will be recorded. They will also be asked to fill in the EQ-5D, AVVQ and CIVIQ scores.

Follow-up at 6 Months

At the 6 months follow-up, patients will be examined and their VCSS will be recorded. They will also be asked to fill the EQ-5D, AVVQ and the CIVIQ scores. They will have a venous Duplex scan to determine occlusion of the treated vein.

Sample Size and Study Duration

We estimated the sample size needed to observe a difference of at least 10mm in the VAS score, with a standard deviation of 20mm. With power at 90% and 5% significance equivalence, we would need to recruit 174 patients (87 per group).

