Appendix 2: Aberdeen Varicose Vein Questionnaire

[figure not shown]
YOUR VARICOSE VEINS

1. Please draw in your varicose veins in the diagram(s) below:-

Legs viewed
from front

Legs viewed
from back

2. In the last two weeks, for how many days did your varicose veins cause you pain or ache?

(Please tick one box for each leg)

	R Leg	L Leg
None at all		
Between 1 and 5 days		
Between 6 and 10 days		
For more than 10 days		

3. During the last two weeks, on how many days did you take painkilling tablets for your varicose veins?

(Please tick one box for each leg)

	R Leg	L Leg
None at all		
Between 1 and 5 days		
Between 6 and 10 days		
For more than 10 days		

- 4. In the last two weeks, how much ankle swelling have you had?**
(Please tick one box)
- | | | |
|--|--------------------------|--|
| None at all |  | |
| Slight ankle swelling |  | |
| Moderate ankle swelling (eg. causing you to sit with your feet up whenever possible) |  | |
| Severe ankle swelling (eg. causing you difficulty putting on your shoes) |  | |
-
- 5. In the last two weeks, have you worn support stockings or tights?**
(Please tick one box for each leg)
- | | R Leg | L Leg |
|--|--------------------------|--------------------------|
| No |  |  |
| Yes, those I bought myself without a doctor's prescription |  |  |
| Yes, those my doctor prescribed for me which I wear occasionally |  |  |
| Yes, those my doctor prescribed for me which I wear every day |  |  |
-
- 6. In the last two weeks, have you had any itching in association with your varicose veins?**
(Please tick one box for each leg)
- | | R Leg | L Leg |
|-------------------------------|--------------------------|--------------------------|
| No |  |  |

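### The cost-effectiveness objective is weakly supported: no EQ-5D falls in the week stockings are worn, and health-care use is recorded only incidentally

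*Combined protocol and SAP*

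**What the plan says.** The list under Secondary Objective includes "Comparison of the cost effectiveness of the intervention", and the Summary says that cost effectiveness will be assessed. No economic method, perspective, tariff or unit-cost source is described.

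**Utility.** The same list sets out "The quality of life scores at baseline, 2 weeks and 6 months using the EQ-5D, AVVQ and CIVIQ scores". The EQ-5D form in Appendix 1 asks patients to "please tick the ONE box that best describes your health TODAY".

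**Exposure.** Under Intervention: "Patients randomised to group A will be asked to wear compression stockings for 1 week".

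**Contacts.** Under Follow-up: "Patients will be followed up in the outpatient clinic at 2 weeks and 6 months". The diary (Appendices 9 and 10) holds a daily pain score for days 0 to 10, the day of return to normal activities, the day of return to work and the day stockings were stopped. It has no EQ-5D.

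**Resource use.** Neither visit description mentions a resource-use form. Related items appear elsewhere:
- AVVQ question 3 (Appendix 2) asks "During the last two weeks, on how many days did you take painkilling tablets for your varicose veins", answered in bands.
- AVVQ question 5 asks about stockings or tights worn in the last two weeks, and whether they were self-bought or prescribed.
- AVVQ question 8 asks whether an ankle rash or eczema needs treatment from a doctor or district nurse.
- Hospitalisation is a criterion for a serious adverse event.

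**The concern.** The Background points to the first week as the period when compression may matter. One cited trial, of 2 against 7 days of stockings, found better pain, physical function and vitality at 1 week with longer wear, and no difference at 6 weeks. The other, of stockings against none, found a pain difference up to day 7 that was absent by week 6, and more analgesic use without stockings.

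A same-day utility measure first repeated about a week after the stockings come off cannot register an effect that has gone by then, whether that effect is a benefit or the burden of wearing them. On the cost side, an extra GP call or nurse visit for pain, or a further vein procedure, has no listed place to be counted. Data of both kinds are lost if they are not collected at the time.

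**Working it through.** The plan states no figure for cost effectiveness, so there is none to reproduce. The sample size (87 per group for the pain score) is not affected by this point.

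**Inputs from the plan.** EQ-5D at day 0, day 14 and 6 months (taken as day 182); same-day recall; stockings for 7 days.

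**Assumptions, as the plan gives no values.** A between-group utility difference d of 0.05, 0.10 or 0.15 during days 0 to 7; no difference at baseline, day 14 or day 182.

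**Step 1: the true QALY difference.** If the difference ends at day 7, it is d × 7 / 365.25:
- d = 0.05: 0.0010
- d = 0.10: 0.0019
- d = 0.15: 0.0029

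If it fades linearly from day 7 to day 14, it is d × (7 + 7/2) / 365.25 = d × 10.5 / 365.25, or 0.0014, 0.0029 and 0.0043.

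**Step 2: what the planned schedule records.** With trapezoids on days 0, 14 and 182, the weights in years are:
- day 0: (14/2) / 365.25 = 0.019
- day 14: (14/2 + 168/2) / 365.25 = 91 / 365.25 = 0.249
- day 182: (168/2) / 365.25 = 0.230

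The difference is zero at all three points, so the recorded QALY difference is 0 for every d and both profiles. By contrast, a difference of only 0.01 at day 14 is credited as 0.01 × 0.249 = 0.0025 QALY. Effects that last to day 14 are therefore counted.

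**Step 3: with an EQ-5D at day 7.** On days 0, 7, 14 and 182:
- day 7 weight: (7/2 + 7/2) / 365.25 = 7 / 365.25 = 0.019
- day 14 weight: (7/2 + 168/2) / 365.25 = 87.5 / 365.25 = 0.240

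The recorded difference becomes d × 7 / 365.25. That is the whole of the true value if the effect ends at day 7, and 7 / 10.5 = two thirds of it if the effect fades to day 14.

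**Step 4: cost items against what is collected.**

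| Item | Where recorded | Gap |
|---|---|---|
| Painkillers | AVVQ question 3 | Banded days; no drug or dose; at 6 months covers only the last two weeks |
| Hosiery | AVVQ question 5, diary | Banded; two-week window |
| Work | Diary | Days 0 to 10, then a single open category |
| Doctor or nurse treatment | AVVQ question 8 | Ankle rash or eczema only; no count |
| Hospital stay | Serious adverse event report | Only if it qualifies as one |
| GP, nurse and outpatient contacts | None listed | No count |
| Further vein treatment | None listed | No count |

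**The case against.** The strongest reply is that the plan promises cost effectiveness, not QALYs. The daily pain score covers the whole stocking week, so cost per unit of pain is possible. CIVIQ looks back four weeks and most AVVQ symptom questions look back two, so the 2-week visit does capture week-1 quality of life, though not as a utility. This stands, and it rules out several stronger readings.

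- **A reader might infer that the objective cannot be answered.** A limited analysis is possible. Its QALY would miss a transient week-1 effect and its costs would be incomplete.
- **A reader might infer that no visit records resource use.** The AVVQ is completed at both visits. At 2 weeks its painkiller question covers the stocking week.
- **A reader might infer that week 1 holds the only plausible QALY difference.** The Background gives no result at day 14 for either trial. One of them compared two durations of wear, and the other reported a satisfaction difference still present at 6 weeks (4.59 against 4.18).
- **A reader might infer that the day-7 form would cure the imprecision of the QALY.** It would not. With an assumed EQ-5D SD of 0.2 and 87 per group, the day-14 value alone contributes a standard error of 0.2 × √(2/87) × 0.249 = 0.0076 QALY. With a day-7 form the weight is 0.240 and the figure is 0.0073. That noise comes from the 6-month horizon at this sample size, so it is no argument for the change.

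Appendix 3 and the Appendix 11 flowchart are not visible in the supplied text, so a resource-use form there cannot be excluded.

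**Conclusion.** The point holds as a weakness of one secondary objective. As scheduled, the EQ-5D gives zero weight to a utility difference confined to the stocking week and gone by day 14. That omits about 0.0010 to 0.0029 QALY for assumed differences of 0.05 to 0.15 over 7 days, or up to 0.0043 if the effect fades over the second week. Resource use is recorded only incidentally, and the visit descriptions list no count of health-care contacts or further vein treatment.

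The utility differences are assumptions. The plan gives no stocking price either, so it cannot be shown that the missing amount would decide the economic conclusion. The case for acting is that the loss is avoidable and cannot be made good later. The sample size and the primary endpoint are unaffected.

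**What to change.** 1. Add one EQ-5D page to the existing 10-day diary for day 7, and optionally another for day 3. State that these values enter the area-under-curve QALY.
2. Add a short checklist at the 2-week and 6-month visits: GP, nurse and hospital contacts, and further vein treatment, since the last visit.
3. Use the existing AVVQ and diary items for painkillers, hosiery and return to work, without asking again.

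The cost is one or two diary pages, a brief checklist and a few minutes of each patient's time. No extra visit is needed, and sample size and treatment do not change. If Appendix 3 or the flowchart already contains a resource-use form, step 2 reduces to checking that it covers these items.

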Appendix 2: Aberdeen Varicose Vein Questionnaire

[figure not shown]
YOUR VARICOSE VEINS

1. Please draw in your varicose veins in the diagram(s) below:-

Legs viewed
from front

Legs viewed
from back

2. In the last two weeks, for how many days did your varicose veins cause you pain or ache?

(Please tick one box for each leg)

	R Leg	L Leg
None at all		
Between 1 and 5 days		
Between 6 and 10 days		
For more than 10 days		

3. During the last two weeks, on how many days did you take painkilling tablets for your varicose veins?

(Please tick one box for each leg)

	R Leg	L Leg
None at all		
Between 1 and 5 days		
Between 6 and 10 days		
For more than 10 days		

- 4. In the last two weeks, how much ankle swelling have you had?**
(Please tick one box)
- | | | |
|--|--------------------------|--|
| None at all |  | |
| Slight ankle swelling |  | |
| Moderate ankle swelling (eg. causing you to sit with your feet up whenever possible) |  | |
| Severe ankle swelling (eg. causing you difficulty putting on your shoes) |  | |
-
- 5. In the last two weeks, have you worn support stockings or tights?**
(Please tick one box for each leg)
- | | R Leg | L Leg |
|--|--------------------------|--------------------------|
| No |  |  |
| Yes, those I bought myself without a doctor's prescription |  |  |
| Yes, those my doctor prescribed for me which I wear occasionally |  |  |
| Yes, those my doctor prescribed for me which I wear every day |  |  |
-
- 6. In the last two weeks, have you had any itching in association with your varicose veins?**
(Please tick one box for each leg)
- | | R Leg | L Leg |
|-------------------------------|--------------------------|--------------------------|
| No |  |  |
| Yes, but only above the knee |  |  |
| Yes, but only below the knee |  |  |
| Both above and below the knee |  |  |
-
- 7. Do you have purple discolouration caused by tiny blood vessels in the skin, in association with your varicose veins?**
(Please tick one box for each leg)
- | | R Leg | L Leg |
|-----|--------------------------|--------------------------|
| No |  |  |
| Yes |  |  |
-
- 8. Do you have a rash or eczema in the area of your ankle?**
(Please tick one box for each leg)
- | | R Leg | L Leg |
|--|--------------------------|--------------------------|
| No |  |  |
| Yes, but it does not require any treatment from a doctor or district nurse |  |  |
| Yes, and it requires treatment from my doctor or district nurse |  |  |

9. **Do you have a skin ulcer associated with your varicose veins?**
(Please tick one box for each leg)
- | | R Leg | L Leg |
|-----|--------------------------|--------------------------|
| No |  |  |
| Yes |  |  |
10. **Does the appearance of your varicose veins cause you concern?**
(Please tick one box)
- | | | |
|---|----|--------------------------|
| | No |  |
| Yes, their appearance causes me slight concern | |  |
| Yes, their appearance causes me moderate concern | |  |
| Yes, their appearance causes me a great deal of concern | |  |
11. **Does the appearance of your varicose veins influence your choice of clothing including tights?**
(Please tick one box)
- | | | |
|--|--------------|--------------------------|
| | No |  |
| | Occasionally |  |
| | Often |  |
| | Always |  |
12. **During the last two weeks, have your varicose veins interfered with your work/ housework or other daily activities?**
(Please tick one box)
- | | | |
|--|----|--------------------------|
| | No |  |
| I have been able to work but my work has suffered to a slight extent | |  |
| I have been able to work but my work has suffered to a moderate extent | |  |
| My veins have prevented me from working one day or more | |  |
13. **During the last two weeks, have your varicose veins interfered with your leisure activities (including sport, hobbies and social life)?**
(Please tick one box)
- | | | |
|---|----|--------------------------|
| | No |  |
| Yes, my enjoyment has suffered to a slight extent | |  |
| Yes, my enjoyment has suffered to a moderate extent | |  |
| Yes, my veins have prevented me taking part in any leisure activities | |  |

Appendix 4: Clinical assessment of Varicose Veins

Hospital Number-----	MALE	FEMALE	
Date of birth-----	Number of Pregnancies		
Age -----	Weight/ Kg		
Occupation-----	BMI>30	Yes	No
Date-----	OCP or HRT	Yes	No
	Smoker	Yes	No
Past Medical History			
	Yes No	Yes	No
Bleeding disorder DVT/PE	IHD		Leg ulcers
Diabetes	Hypertension		

Medications

Previous treatment to Varicose Veins

Side	Site	Date	Treatment type

Appendix 5: Pre Operative Clinical Assessment

Score	Definition
0	Asymptomatic
1	Symptomatic, but able to carry out usual activities with out compressive therapy
2	Able to carry out usual activities only with compressive therapy and/or limb elevation
3	Unable to carry out usual activities even with compression and/or elevation
	Usual activities = patients activities before the onset of disability due to venous disease

Appendix 6: Venous Clinical Severity Score (VCSS)

Please indicate right or left leg or bilateral (R, L or B)

	Absent	Mild	Moderate	Severe
Pain	None	Occasional, non/ no analgesia restricting	With moderate activity, occasional analgesia	Daily, severe limitations, regular analgesia
Varicose veins>4mm	None	Few	Multiple GSV	Extensive GSV and LSV
Venous oedema	None	Evening/ankle	Afternoon/ above knee	Morning/requiring elevation
Skin pigmentation	None	Limited and old/brown	Diffuse lower third/ purple	Wide/ purple
Inflammation	None	Mild cellulitis in marginal area	Moderate involving most of gaiter area	Severe cellulitis or significant eczema
Induration	None	Focal <5cm	Medial or lateral less than lower 1/3	1/3 of lower leg or more
Number of active ulcers	0	1	2	3
Active ulcer duration	None	<3 months	>3 months <12 months	>12 months
Active ulcer diameter(cm)	None	<2	2-6	>6
Compression	Not used or non compliant	Intermittent use	Stockings worn most days	Stockings worn daily
Total				

Appendix 7: Clinical-Etiology-Anatomy-Pathophysiology (CEAP Classification)

Clinical	0	1A	1S	2A	2S	3A	3S	4aA	4aS	4bA	4bS	5A	5S	6
Etiology	Congenital			Primary			Secondary			No venous cause identified				
Anatomy	Superficial			Deep			Perforating			No venous location identified				
Pathology	Reflux			Obstruction			Both			No venous pathology identified				

Class 0 No visible or palpable veins

Class 1 Telangiectasia, reticular veins
ulceration

Class 2 Varicose Veins

Class 3 Oedema without skin changes

Class 4 Skin changes ascribed to venous disease

4a) Pigmentation or eczema

4b) Lipodermatosclerosis or atrophie blanche

Class 5 Skin changes and healed
ulceration

Class 6 Active venous ulcers

A= Asymptomatic

S= Symptomatic

Appendix 8

C I V I Q-14

SELF-QUESTIONNAIRE PATIENTS

In English language for UK

Many people complain of leg pain. We would like to find out how often these leg problems occur and to what extent they affect the everyday lives of those who suffer from them.

Below you will find a list of symptoms, sensations or types of discomfort that you may be experiencing and which may make everyday life hard to bear to a greater or lesser extent. **For each symptom, sensation, or type of discomfort listed, we would like you to answer in the following way:**

Please indicate if you have experienced what is described in each sentence, and if the answer is 'yes', how **intense** it was. There are five possible answers, and we would like you to circle the one which best describes your situation.

Circle 1 if you feel the symptom, sensation of discomfort described does not apply to you

Circle 2, 3, 4 or 5 if you have felt it to a greater or lesser extent

QUALITY OF LIFE WITH VENOUS INSUFFICIENCY

- 1)** During the past four weeks, have you had any **pain** in your **ankles** or **legs**, and how severe has this pain been?
Circle the number that applies to you.

No pain	Slight pain	Moderate pain	Considerable pain	Severe pain
1	2	3	4	5

- 2)** During the past four weeks, how much trouble have you experienced at **work** or during your **usual daily activities because of your leg problems**?
Circle the number that applies to you.

No trouble	Slight trouble	Moderate trouble	Considerable trouble	Severe trouble
1	2	3	4	5

- 3)** During the past four weeks, have you **slept badly** because of your leg problems, and how often?
Circle the number that applies to you.

Never	Rarely	Fairly often	Very often	Every night
1	2	3	4	5

During the past four weeks, how much **trouble** have you experienced **carrying out the actions and activities** listed below **because of your leg problems?**

For each statement in the table below, indicate how much trouble you have experienced by circling the number chosen.

	No trouble	Slight trouble	Moderate trouble	Considerable trouble	Could not do it
4) Climbing several flights of stairs	1	2	3	4	5
5) Crouching, Kneeling down	1	2	3	4	5
6) Walking at a brisk pace	1	2	3	4	5
7) Going out for the evening, going to a wedding, a party, a cocktail party...	1	2	3	4	5
8) Playing a sport, exerting yourself physically	1	2	3	4	5

Leg problems can also affect your mood. How closely do the following statements correspond to what you have felt during the past four weeks?

For each statement in the table below, circle the number that applies to you.

	Not at all	A little	Moderately	A lot	Completely
9) I have felt nervous/tense	1	2	3	4	5
10) I have felt I am a burden	1	2	3	4	5
11) I have felt embarrassed about showing my legs	1	2	3	4	5
12) I have become irritated easily	1	2	3	4	5
13) I have felt as if I am handicapped	1	2	3	4	5
14) I have not felt like going out	1	2	3	4	5

